#### Purpose of the Study

There is an unmet need to identify an optimal perioperative opioid regimen for common pediatric surgeries that would reduce postoperative pain to acceptable levels without untoward side effects, reduce post-discharge opioid use, and enable reduced postop opioid prescribing. Such a standardized intra-operative opioid regimen pediatric tonsillectomy is long overdue and will require an innovative approach. Methadone is a cost effective, efficacious, and long-acting opioid with an elimination half-life of 24-36 hours. A single intraoperative dose has been used safely and effectively in multiple adult surgical procedures and populations, reduces both postoperative pain and opioid consumption, and increases patient satisfaction compared with shorter acting opioids. Methadone has been used in major pediatric surgeries with encouraging results, but it has not been studied in pediatric tonsillectomy.

Our central hypothesis is that a single intraoperative dose of methadone provides superior pain control and reduction of postop opioid use compared to current routinely used short-acting opioids. To investigate this, we propose a prospective, double blind, randomized, controlled, dose-finding pilot study of single-dose intraoperative IV methadone, compared with short-duration opioids (fentanyl, hydromorphone) in 60 children >=3 and <18 years old undergoing elective tonsillectomy. The primary research goal is to determine an optimal intraoperative methadone dose, and secondarily to assess pain and postop opioid utilization in PACU and for 7 days after surgery. We will test this hypothesis and accomplish our proposal objective, with the following two specific aims:

- 1. Determine an optimal intraoperative dose of intravenous methadone. Prior pediatric and adult literature have published dosing regimens between 0.1mg/kg and 0.3mg/kg for various operations. Our working hypothesis is that a single methadone dose of 0.1mg/kg to 0.2mg/kg of age based ideal body weight can be identified, that will result in less postoperative pain and opioid use. This is designed as a dose-escalation pilot, with anticipated need for a cohort to receive a higher dose than the initial 0.1 mg/kg.
- 2. Analyze post-operative outcomes including post-operative opioid utilization and pain scores in the first 7 days after surgery. Our working hypothesis is that those patients who receive a single intraoperative methadone dose will have statistically less postoperative opioid utilization and pain scores, without a greater incidence in adverse events (respiratory depression or excessive sedation).

#### Background & Significance

Pain is ubiquitous in pediatrics as every infant, child and adolescent will experience it in early life. Yet, pain in children remains a prevalent concern because it is often under-recognized and

under-treated and has the potential to result in life-long comorbidities. There is strong evidence that untreated pediatric pain incurs a high risk for the subsequent development of persistent pain, disability, and psychological disorders in adulthood. In fact, approximately 20% of adult chronic pain patients report a history of poorly managed pain in childhood or adolescence.

One common source of pediatric pain is a direct result of invasive procedures. Each year in the United States, hundreds of thousands of children undergo elective tonsillectomies. Pain after pediatric tonsillectomy is frequent, severe and often insufficiently treated which can lead to post-operative complications such as poor oral intake, dehydration and prolonged recovery. In 2019, The American Academy of Otolaryngology published a Clinical Practice Guideline which included a strong recommendation for the use of non-opioid anti-inflammatory medications for pain management following tonsillectomy in children. However, there is no further guidance for surgeons about the use of other opioids, including type, dose, duration or frequency. We commonly use short acting opioids (fentanyl and hydromorphone) at the discretion of the anesthesiologist in line with standard of care practices to manage both intraoperative and post operative pain following pediatric tonsillectomy. Intraoperative methadone is also used as standard of care practice in pediatric patients (3-18 year olds) for other routine procedures. Yet anesthesiologists and surgeons have published literature showing significant variability amongst perioperative opioid practices and there is a growing movement to reduce or remove opioids from post-tonsillectomy algorithms entirely.

It's widely recognized that standardization of a perioperative opioid regimen for pediatric tonsillectomy pain is long overdue. The lack of guidance both intraoperatively and post operatively results in a haphazard approach to analgesia which directly results in the inadequate treatment of moderate to severe pain. There are also unique considerations for pain management in children that must be considered. Most notably, the task of providing sufficient analgesia to a child often becomes the task of the parent or caregiver. There is a well-documented tendency for parents to under-treat despite pain behaviors for a variety of reasons. Conversely, studies have shown that teenagers are more likely to receive refills on their initial post-operative opioid prescription which places them at risk for opioid misuse, abuse or diversion. This is supported by evidence that shows that millions of 12 to 17-year-olds self-report prescription opioid misuse annually, and at least 25% of these adolescents initially receive their opioids from their medical provider. Commonly left-over opioids are typically not locked in storage, not returned or disposed of and remain available for misuse by patients, families or diversion.

Therefore, it is conceivable that the use of a long-acting opioid such as methadone could have multiple benefits in pediatrics including 1. significantly decreasing pain after surgery, 2. reducing barriers to adequate analgesia in young children, 3. reducing surgeon over-prescribing of discharge take-home opioids, 4. reducing the pool of left-over opioids available for misuse or diversion, and 5. mitigating risks associated with opioid use in the adolescent population.

#### **Design & Procedures**

Study Design: Single center, randomized, double blind, parallel-group dose escalation investigation. All patients will receive standard monitoring for anesthesia and postoperative care. Surgical and anesthesia care (except for intraoperative opioid management) are not altered for study purposes. Subjects are randomized 2:1 to either long-duration (methadone) or short-duration opioid (fentanyl, hydromorphone). The use of any short acting opioid (ie: fentanyl, hydromorphone or both) is considered the control group and total dose, timing of administration, frequency of administration, and dose per administration of either/both short acting opioids will be administered at the discretion of the anesthesiologist as per standard of care practice. Because methadone analgesia for pediatric tonsillectomy has not previously been studied, this pilot study will use escalating dose groups to determine the optimal dose for this procedure. In order to achieve this, our trial design will include two periods. In the first period, we will randomly assign 20 patients to methadone 0.1 mg/kg and 10 patients to typical shortduration opioid (controls). An interim analysis will be conducted to determine if we should escalate to the higher dose of methadone. Methadone dose escalation to 0.15mg/kg age ideal body weight will occur if there is no difference in non-methadone PACU opioid use and no increased adverse events. If proceeding to the second period, we will recruit 20 patients for 0.15 mg/kg methadone and 10 patients as controls. Sample size for this pilot investigation was based on prior studies.

Defining an optimal dose of methadone is a crucial aim of this study, which will allow for future investigations, but is not a primary or secondary outcome. The dose finding nature of this study requires interim assessments after each methadone dose cohort. After the first 20 methadone subjects at 0.1mg/kg age ideal body weight, there will be a planned partial analysis of PACU opioid use. Methadone dose escalation to 0.15mg/kg age ideal body weight will occur if there is no difference in non-methadone PACU opioid use and no increased adverse events. Sample size for this pilot investigation was based on prior studies.

Pre-operative, Intra-operative, Post-operative Care: Anesthesia and surgical care are not altered for this study except for randomization to the study drug. Oral or IV midazolam for anxiolysis may be given at standard dosing. Anesthetic induction via inhaled sevoflurane or intravenous agents are to be given at the anesthesiologist's discretion.

Patients in the short-duration opioid group receive short-duration opioids (IV fentanyl and/or hydromorphone), given as needed throughout the intraoperative period, per usual practice at practitioner's discretion. Patients in the long-duration opioid group receive IV methadone HCl at 0.1mg/kg. These subjects receive methadone as their only intraoperative opioid, given as a single bolus at anesthetic induction. If needed, a second cohort will receive or 0.15mg/kg of age-based ideal body weight. Following extubation, patients may receive incremental doses of

0.1mg/kg up to a maximum of 0.5mg/kg of dexmedetomidine (dosed at age-based ideal body weight) for sedation if needed, contingent upon adequate ventilatory rate.

For analgesia in the Post-Anesthesia Care Unit (PACU), patients in both groups may receive typical short-duration opioids (fentanyl or hydromorphone) as per usual routine care. It is not necessary that patients receive the same opioid postoperatively as intraoperatively. Post-op opioids orders are written by the pediatric anesthesiologist and opioids are given by PACU nurses per standard practice, based on developmentally appropriate pain scales (FLACC, Wong-Baker Faces, VAS) and institutional practice.

Pain scores via developmentally appropriate and validated pediatric pain scales will be confirmed by a blinded research coordinator OR a blinded secondary pediatric PACU nurse and charted in the EMR prior to administration of opioid analgesics. Adverse events will be recorded by a research coordinator who is blinded to randomization allocation and include: Respiratory depression (respiratory rate <10/min), reintubation, decreased oxygen saturation <85% for 30 seconds, excessive sedation (Pasero Opioid-induced Sedation Scale (POSS) score 3>1 hour, 4>15 minutes), unexpected PICU admission, and vomiting in PACU.

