#### Protections against Risk:

- i) Eligibility criteria exclude patients with known renal or hepatic disease, which may affect opioid disposition, pregnant females, those with severe sleep apnea with apnea hypopnea index > 10 and those who require planned ICU admission post operatively.
- ii) Methadone dosing is fixed, using age based ideal body weight, rather than actual body weight, to obviate risk of excessive dosing due to obesity.
- iii) Dose escalation will only occur if there are no adverse events in the initial dosing group

- iv) If nausea and/or vomiting occur, patients will be treated using the standard of care for all post-anesthesia nausea and vomiting. Respiratory depression with a respiratory rate <10 breaths/minute or hypoxia with oxygen saturation less than 85% for > 30 seconds will be monitored closely. If treatment is required, naloxone will be used. Patients will be routinely monitored by pulse oximetry, and receive supplemental oxygen if dictated, according to standard anesthesia practice.
- v) Research subjects will receive pre-operative, intra-operative and post-operative routine monitoring by anesthesiology and nursing staff.
- vi) The risk of breach of protected health information will be minimized by limiting the number of people within the research group who have access to identified data which will be described in the data monitoring safety plan.

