### **Data Analysis & Statistical Considerations**

Descriptive statistics for each treatment group will be computed for patient demographic and characteristic variables. Since our randomization scheme will have balanced the age effect between treatment groups, we anticipate the demographic and patient characteristic variables will be balanced across groups. For the continuous outcome measures (primary and most of secondary outcomes), we will conduct two-sample t-test to test the outcome difference (e.g., total OME difference) between treatment groups. For categorical outcomes (e.g., PACU side effects and adverse events), chi-square or Fisher exact tests will be applied as appropriate. Considering this is a pilot study for dose finding, we will relax the significance threshold to 0.1 for the interim analysis. Using the primary outcome, total OME/kg as an example, a two-sample t-test will be performed for comparing total OME difference between 20 methadone (0.1mg/kg) treated patients to 10 controls based on significance threshold of 0.10. If methadone showed significant effect on the outcome measure, the higher dose arm (0.15 mg/kg age ideal body weight) will be pursued. In the final analysis, similarly, two-sample test

will be used to test the total OME difference between methadone and control groups for both dose levels. To correct for multiple testing, the significance threshold in the final analysis will be set at 0.025. If there are covariates showing significant difference between treatment groups, we will perform multivariable linear regression analysis to test the treatment effect after adjusting for one selected covariate and examine if the treatment effect remains the same as that found in the two-sample t-test. The reason to restrict to one covariate in the model was to avoid model overfitting considering there will be only 20 samples per group. Similar analysis strategy will be applied to other outcome measures.

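### The interim rule for escalating to 0.15 mg/kg is written in two opposite directions, with two different adverse-event conditions

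*Combined protocol and SAP*

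**What the plan says.** **Efficacy trigger.** The Study Design text under Design & Procedures states twice that escalation to 0.15 mg/kg "will occur if there is no difference in non-methadone PACU opioid use and no increased adverse events". Data Analysis & Statistical Considerations sets the interim threshold at 0.10 and then says: "If methadone showed significant effect on the outcome measure, the higher dose arm (0.15 mg/kg age ideal body weight) will be pursued".

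**Decision variable.** The design text says "there will be a planned partial analysis of PACU opioid use". The statistics text says: "Using the primary outcome, total OME/kg as an example, a two-sample t-test will be performed for comparing total OME difference". That outcome is offered as an example and carries no time window there.

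**Adverse events.** The design text requires no increase. Protections against Risk is stricter: "Dose escalation will only occur if there are no adverse events in the initial dosing group". The statistics section has no safety condition. The adverse events to be recorded run from respiratory depression to "unexpected PICU admission, and vomiting in PACU".

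**Supporting text.** Purpose of the Study speaks of an "anticipated need for a cohort to receive a higher dose than the initial 0.1 mg/kg", and the care description under Design & Procedures says "If needed, a second cohort will receive" the higher dose. Both fit escalation when 0.1 mg/kg proves insufficient. The Power calculation makes the final two-dose analysis conditional on being able to move on to the higher dose, which sounds more like the statistics section. The Interim Analysis text under Unblinding Procedures says that the interim decides and that the study then continues at 0.1 or 0.15 mg/kg. It gives no criterion.

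**The concern.** A rule that escalates when the first dose shows no difference is a search for an adequate dose. A rule that escalates when the first dose shows a significant effect is a proof-of-activity gate. Either can be defended, but on the same outcome they give opposite instructions: a clear interim benefit means escalate under one and stay under the other, and a null result means the reverse.

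The rule decides whether 20 children receive the higher dose and whether the 0.15 mg/kg comparison exists at all. The plan describes finding the optimal dose as a crucial aim, and Study Interventions cites the escalation criteria as a protection when arguing for IND exemption. A statistician and an investigator who each follow their own section would reach different decisions from the same data. If the conflict is noticed only after the interim unblinding, the direction could be chosen with the result in view.

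**Working it through.** **1. Reproduce the plan's figures.** Inputs from the Power calculation: equal-variance two-sample t-test; SD 0.3; interim 20 vs 10, difference 0.3, alpha 0.10; final 20 vs 20, difference 0.31, alpha 0.025. Sidedness is not stated.

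- Interim standard error = 0.3 × √(1/20 + 1/10) = 0.3 × 0.3873 = 0.1162. Noncentrality = 0.3 / 0.1162 = 2.58 on 28 df. Power from the noncentral t is 0.809 two-sided and 0.897 one-sided. The plan says 80%, so the test is two-sided.
- Final power, two-sided, is 0.820. The plan says 82%.

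The power arithmetic is sound.

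**2. Apply both efficacy rules to that test.** Assumptions: one shared outcome with SD 0.3; no difference means p ≥ 0.10; the safety condition is met. The statistics-section rule then escalates with probability equal to power, and the design-section rule with 1 − power.

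| True difference | Escalate, statistics section | Escalate, design section |
|---|---|---|
| 0 | 10% | 90% |
| 0.1 | 22% | 78% |
| 0.15 | 35% | 65% |
| 0.2 | 51% | 49% |
| 0.3 | 81% | 19% |
| 0.4 | 96% | 4% |

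If only a significant benefit counts in the statistics section, its no-effect figure falls to 5%. The design-section figure is then 90% (p ≥ 0.10 in either direction) or 95% (no significant reduction).

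The two rules switch at an observed difference of t(0.95, 28) × standard error = 1.701 × 0.1162 ≈ 0.198, taking the observed SD as 0.3.

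The 0.809 depends on the SD. At assumed SDs of 0.2, 0.4 and 0.5 it becomes 0.984, 0.597 and 0.447. The opposition between the rules does not depend on the SD.

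**3. Compare the adverse-event conditions.** One child vomiting among 20 on methadone (1/20 = 5%) and one among 10 controls (1/10 = 10%) is no increase over controls, so the design-section condition is met. It is not zero events, so the Protections against Risk condition fails.

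The documents give no event rate, so the following rates are assumed, equal in both arms. The zero-event probability is (1 − q)^20. The design text does not define an increase, so two readings are shown.

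| Assumed rate q | Zero events in 20 | Observed rate not above controls | No significant excess (one-sided Fisher, 0.10) |
|---|---|---|---|
| 5% | 36% | 59% | about 100% |
| 10% | 12% | 56% | 99.6% |
| 20% | 1% | 55% | 97% |

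At an assumed rate of 1% the zero-event condition passes 82% of the time. At the higher rates, the choice of condition could settle the escalation decision by itself.

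**The case against.** The triggers are exact opposites only on a shared variable. If PACU opioid use and total OME/kg are different quantities, the same data could satisfy both. That is correct, and it makes the percentages illustrative. It does not rescue the plan, because two unreconciled rules on two variables still leave the decision undefined.

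The SD of 0.3 is given for total OME, and the design section never equates no difference with p ≥ 0.10. Both points stand and are carried as stated assumptions. Reading no difference as not worse would soften the conflict, but the text does not say that, and a null result would still escalate under one section and not the other.

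The adverse-event conditions are nested: zero events on methadone always implies no increase. A cautious team could treat the stricter one as binding, since it alone is worded as a necessary condition. That is a safe reading, but the plan does not adopt it, and with vomiting on the list it could block escalation for a minor event.

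The supplied text contains no outcome list, so a definition and time window for total OME may sit on a page not available here. The missing window should therefore not be held against the plan. The inconsistent naming remains.

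The 80% is a correct statement of power to detect a difference under either direction. What changes is its meaning for the decision.

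**Conclusion.** The concern holds. The current text contains opposed escalation triggers, two adverse-event conditions that diverge whenever an event occurs without an excess over controls, and two names for the decision variable. No section ranks them.

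On the plan's own interim assumptions, the choice of section moves the chance of escalating between 81% and 19% at a difference of 0.3, and between 10% and 90% with no effect. These figures rest on one shared outcome with SD 0.3, a two-sided test, no difference read as p ≥ 0.10, and the safety condition being met. The contradiction in wording rests on none of them. This must be fixed before the interim analysis.

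**What to change.** Put one identically worded escalation rule in Study Design, Protections against Risk and Data Analysis & Statistical Considerations, and have the Interim Analysis text under Unblinding Procedures refer to it. The rule should state:

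1. the direction that triggers escalation;
2. one decision variable, with its time window;
3. the test and threshold, including what counts as no difference and what happens if methadone patients use significantly more opioid;
4. one adverse-event criterion, naming which of the recorded events count and the comparator, if any.

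The sponsor must confirm the direction and the variable. Purpose of the Study and the care description favour the design-section direction. If that is kept, reverse the sentence in the statistics section: escalate when no significant reduction is shown at 0.10 and the adverse-event criterion is met.

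Reword the interim part of the Power calculation to match. Under that direction, the 80% is roughly the chance of not escalating at a difference of 0.3. Under the other, it is roughly the chance of escalating, provided the safety criterion is met. If the variable becomes PACU opioid use, recheck the SD and the difference.

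The cost is a wording amendment, with no added patients or data. The final-analysis power of 82% is unaffected if total OME remains the outcome.

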### Selection of Subjects

Patient Selection: Patients undergoing tonsillectomy +/- adenoidectomy at Duke University Hospital and Duke Regional Hospital or a Duke Affiliated Ambulatory Surgical Center (including Davis Ambulatory Surgical Center) will be recruited for enrollment. Selection criteria are as follows:

Inclusion Criteria (IC): Children age >=3 and <18 yrs having elective tonsillectomy +/-adenoidectomy with signed, informed consent by parent or legal guardian. Post pubescent females are required to have a negative pregnancy test within 48 hours of surgery. Children >12 years must give assent.

Exclusion Criteria (EC): Patients with any of the following: 1. history of or known liver or kidney disease 2. Consistent daily opioid use for chronic pain (defined as ongoing pain >3 months) 3. severe sleep apnea (Sleep study with Apnea Hypopnea Index (AHI) > 10). 4. planned admission to the Pediatric Intensive Care Unit (PICU) following surgery 5. additional procedures under the same general anesthetic for which outpatient opioids would be prescribed.

Patients undergoing procedures such as PE tubes, nasal endoscopy, Auditory Brain Response tests, imaging studies do not have to be excluded.

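### Dexmedetomidine after extubation is written in mg/kg: if micrograms are meant, both figures are 1000 times too high, so check the protocol page and correct the unit if confirmed

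*Combined protocol and SAP*

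**What the plan says.** The line is in the combined protocol and SAP, Design & Procedures, in the paragraphs on pre-operative, intra-operative and post-operative care. It begins "Following extubation, patients may receive incremental doses of" and, after a break in the extracted text, continues "0.1mg/kg up to a maximum of 0.5mg/kg of dexmedetomidine (dosed at age-based ideal body weight) for sedation if needed". It ends with a condition: "for sedation if needed, contingent upon adequate ventilatory rate".

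The dose is therefore optional, given in steps, scaled to age-based ideal body weight and conditional on breathing. The sentence names no treatment arm. Both figures carry the unit mg/kg.

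Dexmedetomidine appears nowhere else in the documents. No section gives a microgram dose, a reference or a justification for the amount. The same part of the protocol opens by saying "Anesthesia and surgical care are not altered for this study except for randomization to the study drug".

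**The concern.** Micrograms per kilogram is the usual unit for dexmedetomidine. That is general unit knowledge, used here as a stated assumption; the documents do not give it. Against that unit, a step of 0.1 mg/kg and a ceiling of 0.5 mg/kg look like a slip of three orders of magnitude. The numerals 0.1 and 0.5 are not in question.

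Nothing nearby would alert a reader. The paragraph before gives the study drug in the same form ("Patients in the long-duration opioid group receive IV methadone HCl at 0.1mg/kg"), so the dexmedetomidine step looks identical to the methadone dose.

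The stakes are patient safety. This is an explicit dose and maximum for children aged 3 to under 18 who have just been extubated. Elsewhere in the same paragraphs, midazolam is left to standard dosing and induction to the anesthesiologist; here the protocol gives numbers. Study Interventions says that anesthesia providers receive group-specific instructions and are advised on study procedures. If that material repeats the line, a wrong unit could reach the point of care.

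**Working it through.** **Inputs from the protocol (Design & Procedures)**

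- Step as written: 0.1 mg/kg.
- Maximum as written: 0.5 mg/kg.
- Weight basis: age-based ideal body weight.

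**Assumptions (not in the documents)**

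- Intended unit: mcg/kg, numerals unchanged.
- Illustrative ideal body weights: 20 kg, with a range of 15 to 50 kg. The documents give no weights.

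**1. The plan's own figures.** The dose is stated, not derived, so there is no calculation to reproduce. The two numbers fit together: 0.5 / 0.1 = 5 steps to reach the maximum.

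**2. Conversion.** With 1 mg = 1000 mcg:

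- step: 0.1 mg/kg × 1000 = 100 mcg/kg, against an assumed 0.1 mcg/kg;
- maximum: 0.5 mg/kg × 1000 = 500 mcg/kg, against an assumed 0.5 mcg/kg;
- ratio: 100 / 0.1 = 500 / 0.5 = 1000, whatever the weight.

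**3. Absolute amounts** (dose per kg × weight):

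| Assumed weight | Step as written | Maximum as written | Step if mcg/kg | Maximum if mcg/kg |
|---|---|---|---|---|
| 15 kg | 1.5 mg | 7.5 mg | 1.5 mcg | 7.5 mcg |
| 20 kg | 2 mg | 10 mg | 2 mcg | 10 mcg |
| 30 kg | 3 mg | 15 mg | 3 mcg | 15 mcg |
| 50 kg | 5 mg | 25 mg | 5 mcg | 25 mcg |

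**4. Search for a correction elsewhere.** The unit mg/kg occurs 23 times in the text. Of these, 21 are methadone doses and 2 are the dexmedetomidine figures. No other section restates or amends the dexmedetomidine dose. A unit carried over from methadone would explain the line, but the count does not prove it.

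**5. Effect on the statistics.** The power figures in Data Analysis & Statistical Considerations come from a two-sided, two-sample t-test with noncentrality d / (SD × √(1/n₁ + 1/n₂)):

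- interim: 0.3 / (0.3 × √(1/20 + 1/10)) = 2.58, 28 df, alpha 0.1; power 80.9% (stated 80%);
- final: 0.31 / (0.3 × √(1/20 + 1/20)) = 3.27, 38 df, alpha 0.025; power 82.0% (stated 82%).

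Both reproduce, and the dexmedetomidine dose enters neither.

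**The case against.** The strongest objection is that the intended unit cannot be shown from the documents. They contain no microgram dose, label or reference for this drug, and no internal contradiction. The factor of 1000 is only the ratio of the two units and is not evidence that micrograms were meant. This stands, and it is why the point is conditional. The statement that anesthesia care is otherwise unaltered fits usual dosing being intended, but does not settle the unit.

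A second objection is that the point turns on one letter in machine-read text, on a line that follows a break in mid-sentence. A micro sign read as m would produce exactly this wording. That also stands. A reader might argue from the plain keyboard symbols elsewhere, such as those in "Children age >=3 and <18 yrs having elective tonsillectomy +/-adenoidectomy", that the author typed everything by hand and so made the slip. Those characters fit equally well with symbols flattened during extraction, so they do not help.

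A third objection is that the dose is optional, stepwise, tied to adequate ventilation and given under routine anesthesia monitoring by clinicians likely to notice. This lowers the chance of harm. It does not limit the amount: the only stated limit on the dose is the 0.5 mg/kg maximum, which is the figure in doubt.

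Two stronger readings are tempting and should not be adopted.

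- A reader might infer that the error cancels the weight-based safeguard in Protections against Risk. That text reads "Methadone dosing is fixed, using age based ideal body weight, rather than actual body weight, to obviate risk of excessive dosing due to obesity"; it concerns methadone in obesity, and a dexmedetomidine unit does not remove it.
- A reader might set 0.5 mg/kg beside the methadone doses as a measure of risk. Amounts per kilogram of two different drugs are not comparable in that way.

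**Conclusion.** The concern holds conditionally. The text as available sets a step of 0.1 mg/kg and a maximum of 0.5 mg/kg, and nothing elsewhere corrects them. If the protocol page reads mg/kg and the drug is meant to be dosed in mcg/kg, both figures are too high by exactly 1000: a ceiling of 7.5 to 25 mg instead of 7.5 to 25 mcg over assumed weights of 15 to 50 kg. In an explicit pediatric dosing line that has to be fixed. If the page shows a micro sign, the error is zero and the point is withdrawn.

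A reader might infer an established dosing error, or that children would actually receive such doses. The documents support neither: they do not state the intended unit and do not show what any derived instruction says. Nor is this a flaw in the trial's inference, since no endpoint, sample size, alpha or power figure depends on it. Confidence is medium, because the remaining doubt lies in the PDF page and in the unit assumption, not in the arithmetic.

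**What to change.** 1. Look at the Design & Procedures page of the protocol and see whether the dexmedetomidine unit is mg/kg or a micro sign. If it is a micro sign, stop there.
2. If it is mg/kg, ask the investigator and pharmacy to confirm the intended unit.
3. On confirmation, change both figures so that the line permits increments of 0.1 mcg/kg up to a maximum of 0.5 mcg/kg of dexmedetomidine. Keep the numerals, the weight basis and the ventilatory condition.
4. Check any provider instructions or orders that were taken from this line.

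The cost is a look at one page and, if confirmed, a one-line protocol correction with a check of derived material. No statistical text changes.
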